Appendix 1: Murray Score

0-4 severity index of ARDS (total points as per below divided by 4)

a) p/f (with FiO₂ at 100% for 20 mins): $\geq 300=0$ pts, 225-299=1pt, 175-224=2pts, 100-174=3, $<100=4$

-CXR: nl=0, 1 pt per quadrant

b) PEEP: $\leq 5=0$, 6-8=1, 9-11=2, 12-14=3, $\geq 15=4$

c) Compliance: (ml/cmH₂O): $\geq 80=0$, 60-79=1, 40-59=2, 20-39=3, $\leq 19=4$

d) Number of quadrants with infiltr on CXR (1-4)

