For the purpose of identifying the primary endpoint, a brief questionnaire will be completed via phone interview asking after the disability status of the patients 6 months after randomization. Two simple yes/no questions will be answered: is the patient bedbound? Is the patient able to dress and wash his/her self?

G. Study Subjects:

Patients for this study will include patients admitted by any means (either transferred patients or patients entering the hospital via the ED of the ECMO center hospitals) to the ECMO centers involved in the study. In all cases, ECMO will be initiated following randomization at the ECMO study center.

Inclusion criteria will include adult patients (18-65 yo) with severe but potentially reversible hypoxemic respiratory failure despite optimal conventional treatment at the same study centers providing ECMO. Respiratory failure as mentioned will be defined by Murray score >3.0

Exclusion criteria will include duration of high P (>30 cm Ppk) and/or high FiO₂ (>0.8) ventilation for >7 days, intra-cranial bleeding or any other absolute contraindications to heparinization, hypoxemic respiratory failure not fulfilling ARDS definition or hypoxemic respiratory failure deemed irreversible by a study consultant, moribund patients deemed to have minimal chance for survival regardless of chosen intervention as defined by a study consultant. ARDS related hypoxemic respiratory failure implies acute onset of a potentially reversible pathophysiology for which 'lung rest' allowing for low pressure/low FiO₂ vent settings may provide mortality benefit through avoidance of baro/volu-trauma and oxygen toxicity as well as avoidance of any degree of hypoxemia during the acute phase of disease; this is the rationale for excluding nonreversible and chronic hypoxemic respiratory failure.

H. Recruitment of Subjects:

As mentioned above, study subjects will be identified by ARDS diagnosis and by Murray score. Once an ARDS diagnosis is made, Murray score parameters will be monitored every 2 hours, and once Murray score is >2.5 , the patient's primary intensivist will then ask after the consenting family member as to the willingness to speak with a study representative.

I. Confidentiality of Study Data

A unique code will be created for each study participant for identification purposes and for data collection. Data will be secured in a secure location, only accessible by investigators.

J. Potential Conflict of Interest: Unknown.

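### Appendix 1 scores the chest X-ray twice but divides by 4, so adding every printed line can give a Murray score of 5.0 on a stated 0-4 scale and could lead centres to score entry differently

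*Protocol*

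**What the plan says.** Appendix 1 is the only place where the protocol explains how the Murray score is computed. It introduces the score as a "0-4 severity index of ARDS (total points as per below divided by 4"). Five scoring lines follow, four of them lettered:

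- a) P/F ratio, in bands from 0 to 4 points ("225-299=1pt, 175-224=2pts, 100-174=3, $<100=4" for the upper bands);
- an unlettered line beneath a): "CXR: nl=0, 1 pt per quadrant";
- b) PEEP, 0 to 4 points ("6-8=1, 9-11=2, 12-14=3, $\geq 15=4");
- c) compliance, 0 to 4 points ("60-79=1, 40-59=2, 20-39=3, $\leq 19=4");
- "d) Number of quadrants with infiltr on CXR (1-4").

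The score controls entry at three points. Section G (Study Subjects) sets eligibility: "Respiratory failure as mentioned will be defined by Murray score >3.0". Section B, under Study Design, starts the approach to the family above 2.5 and randomises when 3.0 is reached. Section H repeats the 2.5 screening trigger.

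**The concern.** The chest film appears on two of the five scoring lines, and nothing says that it is to be counted once. A coordinator who follows the instruction to total the points listed below it would add both lines, and the result can leave the range given in the same heading. The two lines also differ in scale: the unlettered one gives a normal film zero, while item d starts at 1.

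What is at stake is uniform entry. The Murray score is the only numeric severity threshold, and Section B drops the earlier trial's alternative pH criterion so that the population is defined by this score alone. If one centre counts the film once and another counts it twice, the two apply different thresholds under the same number. Scoring for eligibility belongs in the protocol, so a separate statistical analysis plan would not be expected to repair it.

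**Working it through.** **Inputs (Appendix 1 and Sections B and G).** P/F, PEEP and compliance each score 0 to 4. The chest film scores x = number of affected quadrants, 0 to 4. The divisor is 4. The thresholds are >2.5 (screening), 3.0 (randomisation) and >3.0 (eligibility).

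**Step 1: reproduce the stated range.** Take the four lettered items only, with the film counted once.

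- Score = (P/F + PEEP + compliance + x) / 4
- Maximum = (4 + 4 + 4 + 4) / 4 = 16/4 = 4.0
- Minimum = 0/4 = 0 if a normal film scores 0, or 1/4 = 0.25 if item d is read as starting at 1

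The stated upper limit of 4 is reproduced. The stated lower limit of 0 needs the zero that only the unlettered line supplies.

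**Step 2: add every printed line.**

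- Score = (P/F + PEEP + compliance + 2x) / 4
- Maximum = (4 + 4 + 4 + 8) / 4 = 20/4 = 5.0, which contradicts the 0-4 range
- Difference from Step 1 = x/4, that is 0.25 per affected quadrant: 0.5 for two quadrants and 1.0 for four

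**Step 3: effect at the eligibility threshold.** Passing >3.0 needs at least 13 points. Under Step 2 the points are the single-count points plus x, so the lowest single-count total that passes is 13 − x:

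| Affected quadrants x | Lowest single-count points | Single-count score | Score with every line added |
|---|---|---|---|
| 1 | 12 | 3.00 | 3.25 |
| 2 | 11 | 2.75 | 3.25 |
| 3 | 10 | 2.50 | 3.25 |
| 4 | 9 | 2.25 | 3.25 |

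For example, take P/F 175-224 (2 points), PEEP 6-8 (1), compliance 40-59 (2) and four quadrants (4). Counted once this is 9/4 = 2.25, below even the screening trigger. With both X-ray lines added it is 13/4 = 3.25, above the eligibility threshold.

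**Step 4: the other two triggers.** With four quadrants, reaching 3.0 (12 points) needs 12 − 4 = 8 single-count points, a score of 2.00. Passing >2.5 (11 points) needs 11 − 4 = 7, a score of 1.75.

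**Step 5: how much of the scale is affected.** There are 5 × 5 × 5 × 5 = 625 combinations of the four component scores. Enumerating them, 35 exceed 3.0 when the film is counted once and 167 when it is counted twice. These count combinations of scores. They are not patient frequencies, and the protocol gives no distribution from which frequencies could be derived.

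**The case against.** The strongest reply is that the appendix resolves its own ambiguity. It states a 0-4 range, divides by 4 and letters exactly four components, and those four reproduce the upper limit. Reaching 5.0 requires promoting an unlettered dash line to a fifth component against the heading above it. The two X-ray lines can also be read together, with the unlettered one as the scoring key that supplies the zero for item d. On that reading a normal film leaves at most 12/4 = 3.0 from the other components, which does not pass >3.0, so the missing zero in item d admits nobody under that criterion. Section G also has other entry conditions: failure despite optimal conventional treatment, the ARDS definition, and a study consultant's judgement.

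Most of this stands. Four components were almost certainly intended, and many clinicians would score it that way. It does not make the text correct, however. To recover the intended score, the reader must set aside a printed scoring line or recognise it as a key to an item three lines further down, and nothing says so. Nor would the other entry conditions by themselves correct a mis-scored patient. The duplication is not plausibly a product of text extraction, because the two lines have different wording and different scales.

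Two stronger inferences are tempting. A reader might infer that the trial will admit patients well below its severity threshold. The protocol does not support this: it happens only if a centre adds the unlettered line, and nothing shows that any would. A reader might also infer that control mortality would fall below the 70% used for sizing in Section B, Statistical Analysis. The protocol gives no relation between Murray score and mortality, so no such fall can be shown or sized, and the calculation of 132 per group does not use the score.

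**Conclusion.** Appendix 1 is wrong as written. It scores the chest film on two lines with different scales, and following its instruction to the letter gives a maximum of 5.0 on a scale stated to end at 4. The possible error is 0.25 per affected quadrant, up to 1.0. That is enough to carry a single-count 2.25 past the >3.0 threshold.

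The consequence is conditional. It assumes that at least one centre adds all five lines, whereas the heading, divisor and lettering point to four components. The finding is therefore a risk of inconsistent scoring between centres, not a demonstrated lowering of the threshold. It is worth correcting because this appendix alone defines the score behind screening, randomisation and eligibility in a multi-centre trial, and the correction is very cheap. The difference between a randomisation trigger of 3.0 and an eligibility criterion of >3.0 is a separate matter and does not bear on this conclusion.

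**What to change.** In Appendix 1, merge the two X-ray lines into one component scored from 0 (normal film) to 4 (four quadrants affected), one point per quadrant. State that the score is the sum of four components (P/F, chest X-ray, PEEP and compliance), maximum 16 points, divided by 4, giving a range of 0 to 4. The worksheet or case report form used at the centres should carry the same four items.

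No threshold, treatment rule or sample size changes. The cost is an editorial correction to the appendix, made before the first patient is screened.

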Appendix 2: Stratification guidelines

- a) Age (18-30, 31-45, 46-65)
- b) Hours of high P / high FiO₂ ventilation (0-48, 49-168)
- c) Number of organs failed (1-2 vs 3 or more); failure defined using SOFA score ≥ 2
 - i. Resp—p/f: $<400=1$, $<300=2$, $<200+\text{vent}=3$, $<100+\text{vent}=4$
 - ii. CNS—GCS: $13-14=1$, $10-12=2$, $6-9=3$, $<6=4$
 - iii. CV—MAP: $<70=1$, $\text{DA}=2$, $\text{DA}>5 / \text{epi}<=0.1 / \text{NE } <=0.1 = 3$, $\text{DA}>15 / \text{epi}>0.1 / \text{NE } >0.1 = 4$
 - iv. Liver—Bili: $1.2-1.9=1$, $2-5.9=2$, $6-11.9=3$, $>12=4$
 - v. Coagulation—Plts: $<150=1$, $<100=2$, $<50=3$, $<20=4$
 - vi. Renal—CRE: $1.2-1.9=1$, $2-3.4=2$, $3.5-4.9$ or uop $<500=3$, <5 or UOP $<200=4$

References

1. Morris et al. Randomized Clinical Trial of Pressure-controlled Inverse Ratio Ventilation and Extracorporeal CO₂ Removal for Adult Respiratory Distress Syndrome. *American Journal of Respiratory and Critical Care Medicine*. Vol 149, No 2. Feb 1994, 295-305.
2. Peek et al. Efficacy and Economic Assessment of Conventional Ventilatory Support Versus Extracorporeal Membrane Oxygenation for Severe Adult Respiratory Failure (CESAR): a Multicentre Randomized Controlled Trial. *The Lancet*. Vol 374. Oct 17, 2009.
3. Peek et al. CESAR Study Protocol. *BMC Health Services Research*. 6:163. Dec 23, 2006.
4. UK Collaborative ECMO Group. The Collaborative UK ECMO Trial: Follow-up to 1 Year of Age. *Pediatrics*. Vol 101. No 4. April 1998.
5. Zaponi et al. Extracorporeal Membrane Oxygenation in Severe Acute Respiratory Failure: A Randomized Prospective Study. *JAMA*. Vol 242. No 20. Nov 16, 1979.

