The study will be a longitudinal, prospective, un-blinded, parallel-arm, multi-center, intention to treat, RCT, composed of centers with adult ECMO experience. Study subjects will include patients aged 18-65 admitted to these centers who are diagnosed with potentially reversible hypoxemic respiratory failure. Upon diagnosis with ARDS at the ECMO center, the components of the Murray score will be monitored every 2 hours. Once a Murray score >2.5 is obtained, the intensive care team will begin to profile the patient for the study and contact a study representative if the patient's consenting family member is willing to speak with them (the consenting family member will provide initial consent, then, once able the patient can choose whether or not to continue with the trial). Data collection for all study members will include demographics, diagnosis leading to ARDS, dates of hospitalization/ intubation/ extubation, dates of transfers/discharges, conditions at discharge, complications, cause of death, vent settings, blood gases, hemodynamic status, APACHE II, Murray lung score. Once a Murray score of 3.0 is obtained, the study subject will be randomized to conventional therapy or to ECMO. Given the large potential for other variables to significantly affect the primary outcome of mortality, randomization will be stratified in a fashion similar to that done in the CESAR trial. Stratification will be performed for age, hours of high P/high FiO₂, and number of organs failed (see Appendix 2).

Conventional therapy will include ARDSnet protocol vent management strategy with vent strategies guided by a pulmonologist. Data collection for the conventional management group will include time course, complications, and success with fulfillment of ARDSnet protocol (low-

volume, low-pressure with $P_{plat} < 30$). For the ECMO group, V-V ECMO with percutaneous cannulation will be used, with standardized lung rest vent settings (P_{pk} 20-25, P_{pl} 10-15, rate 10, FiO_2 30%), and ECMO will be continued until lung recovery is deemed obtained or until apparent irreversible multi-organ failure is attained. Data collection for the ECMO group will include cannulation information, flow, sweep, and pressure rates, and complications information.

c. Statistical Analysis:

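### The renal 4-point band in Appendix 2 has its inequality reversed, so some patients would be randomised in the wrong organ-failure stratum if it is applied as printed

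*Protocol*

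**What the plan says.** The Study Design section of the protocol makes organ failure one of three stratification factors: "Stratification will be performed for age, hours of high P/high FiO₂, and number of organs failed (see Appendix 2". Appendix 2, item c, defines it: "Number of organs failed (1-2 vs 3 or more); failure defined using SOFA score ≥ 2".

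The renal row (c, vi) begins "Renal—CRE: $1.2-1.9=1$, $2-3.4=2$, $3.5-4.9$ or uop $<500=3" and closes with "<5 or UOP $<200=4" for the 4-point band.

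Bilirubin, the other laboratory value in the table that rises with severity, is scored "1.2-1.9=1$, $2-5.9=2$, $6-11.9=3$, $>12=4", so its top band is open upwards. The respiratory row begins "Resp—p/f: $<400=1$, $<300=2". Under Study Subjects, the entry criterion is "Respiratory failure as mentioned will be defined by Murray score >3.0".

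**The concern.** The first three renal bands climb with creatinine, and the fourth should carry on above 4.9. As printed it points the other way, with three results:

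- It overlaps the 1, 2 and 3 point bands, so one creatinine value can have two scores.
- It gives 4 points to values below 1.2, which the other bands leave at 0.
- No band covers creatinine of 5 or more, so such a patient scores only through urine output.

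Four points meets the failure threshold of 2, so a wrong 4 adds one failed organ and a missing 4 removes one. The count decides the stratum at randomisation. If some centres silently correct the sign and others do not, the same stratum label means different things at different centres, on a factor that the protocol chose to control because it may affect the outcome.

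**Working it through.** **Inputs.** All are from the protocol: the renal, respiratory, bilirubin and platelet rows, the failure threshold of 2 and the 1-2 versus 3 or more split (Appendix 2); the Murray items (Appendix 1); the entry criterion (Study Subjects); the sample size (Statistical Analysis).

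**The plan's own figure.** No computed figure in the protocol rests on the renal row. The sample size reproduces without it. With 70% versus 52.5%, two-sided alpha 0.05 and power 80%:

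- Uncorrected: n = [1.960 × √(2 × 0.6125 × 0.3875) + 0.842 × √(0.70 × 0.30 + 0.525 × 0.475)]² / 0.175² = 120.5, so 121.
- With continuity correction: (120.5/4) × [1 + √(1 + 4/(120.5 × 0.175))]² = 131.7, so 132 per group, as stated.

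Organ count does not enter the formula.

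**Step 1: which score applies where bands overlap.** The respiratory row (<400, <300 and so on) and the platelet row (<150, <100, <50, <20) work only if the highest matching score is taken. The same convention is applied to the renal row, with no low urine output.

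| Creatinine | Bands matched as printed | Score as printed | Score if top band is 5 or more |
|---|---|---|---|
| 1.0 | 4 | 4 | 0 |
| 1.5 | 1 and 4 | 4 | 1 |
| 2.5 | 2 and 4 | 4 | 2 |
| 4.0 | 3 and 4 | 4 | 3 |
| 6.0 | none | none | 4 |

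At a threshold of 2, failed or not failed differs only below 2 (falsely failed) and at 5 or more (falsely not failed). Between 2 and 4.9 the kidney counts as failed on both readings. With urine output below 500 it also counts as failed on both.

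**Step 2: the lung counts as failed.** The Murray score is a total divided by 4, so a score above 3.0 needs more than 12 points. The other three items give at most 12, so the P/F item must give at least 1, which means P/F below 300. That is respiratory SOFA 2 or more. At a score of exactly 3.0, the trigger named under Study Design, this could fail only if the other three items were all at their maximum.

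**Step 3: organ count and stratum.** Count = 1 (lung) + k + renal (0 or 1), where k is the number failed among CNS, cardiovascular, liver and coagulation.

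| k | Creatinine below 2: printed / continued band | Creatinine 5 or more: printed / continued band | Stratum |
|---|---|---|---|
| 0 | 2 / 1 | 1 / 2 | 1-2 either way |
| 1 | 3 / 2 | 2 / 3 | changes |
| 2 | 4 / 3 | 3 / 4 | 3 or more either way |

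For k of 3 or 4 the stratum is also 3 or more either way. Only k = 1 changes.

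**Step 4: how many patients.** The documents give no organ-failure frequencies, so these are assumptions: each of the four other organs fails independently with probability q = 0.1 to 0.5; true renal failure r = 20% to 50%; creatinine of 5 or more without low urine output w = 2% to 10% of patients.

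- Share moved = 4q(1 − q)³ × [(1 − r) + w].
- Lowest on the grid (q = 0.5, r = 0.5, w = 0.02): 0.25 × 0.52 = 0.13.
- Highest on the grid (q = 0.3, r = 0.2, w = 0.10): 0.412 × 0.90 = 0.37.

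In both, the part from (1 − r), patients pushed up into 3 or more, is much the larger.

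**The case against.** The best defence is that the slip corrects itself. The scale is named as SOFA, the lower bands rise, and bilirubin closes with an upward sign, so a careful user would see what is meant. That is fair, and it makes literal use at every centre unlikely. It does not remove the problem. The highest-match rule that other rows need gives 4 points to every creatinine below 5, and a form programmed from the table would do the same. Uneven correction across centres is itself a fault.

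A second defence is that the sign may have flipped when the PDF was converted to text. This cannot be excluded for a single character, although other upward signs in the same list came through. It is a reason to check the source page first.

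A reader might go further and infer three things that the documents do not support:

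- *That nearly every patient is in the wrong stratum.* Even if almost all were scored as renal failure, lung plus a false renal failure is 2 organs and stays in 1-2. Patients with two or more other failed organs are in the upper stratum anyway.
- *That the factor stops separating prognosis, or is the most important of the three.* On a literal reading the cut is shifted, not made uninformative, and the protocol does not rank its factors.
- *That the treatment comparison is biased.* The stratum is set before allocation by the same rule for both arms.

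**Conclusion.** The point stands as a minor but real error. The renal row contradicts itself, and nothing elsewhere in the protocol corrects it. Read literally, it changes the stratum only for patients with lung failure, exactly one other failed non-renal organ and no low urine output, and only when creatinine is below 2 (moved up) or 5 or more (moved down).

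The 13% to 37% is an illustration on assumed rates with independent organ failures and literal use everywhere. Where centres correct the sign themselves, the share is smaller but the strata are no longer uniform. The conclusion assumes that the sign is printed this way on the source page.

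The loss is weaker balance on a chosen factor and unreliability in any summary by that stratum. The protocol itself specifies no such analysis.

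**What to change.** Check the renal line against the source page. If the sign is as shown, correct the 4-point band to creatinine of 5 or more, or urine output below 200, so that it continues from 4.9. State that the highest matching score applies wherever bands overlap.

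Do this before the randomisation form is built. At that stage it costs one changed sign and one sentence. Once patients have been allocated, the stratum used for each of them cannot be changed.
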